17.0. Exploratory (Tertiary) Effectiveness Analyses

We will examine the impact of the active interventions on exploratory outcomes using the same proposed approach for secondary outcomes outlined above in Section 15.0.

18.0. Economic Analyses

We will conduct a full economic evaluation of the CBT-based interventions, compared to usual care, using the framework of cost-effectiveness, including the costs of implementation and maintenance, following best practice in economic evaluation.^{26,27} This analysis will be conducted for the Kaiser Permanente clinical sites where the capture of all health care utilization is available through administrative data; inclusion of Essentia Health in these cost analyses is subject to the findings of exploratory analyses related to comprehensiveness of EHR data sources that is being conducted during the UG3 phase. Information on resources used to implement the intervention will come from the trial data collection instruments and from medical office staff, provider interviews, and study staff. We

will include all relevant resources used in the intervention delivery (e.g., training, counseling, fidelity assurance). EHR data will be used to identify and classify health care encounters and prescription medications. Using the framework of cost-effectiveness, we will estimate the incremental cost per additional patient with a MCID in pain severity (30% reduction from baseline), at 12 months, and the Quality-Adjusted Life Year (QALY) gained—utilities will be estimated using the EQ-5D-5L.¹¹

Costs to be collected. Medical care utilization and intervention costs will be considered. Medical care utilization includes pharmacy, outpatient visits (including specialty care), inpatient stays, and referrals, and will be costed using standard costing algorithms^{12,13} and Medicare fee schedules. In addition to total medical care costs, we will also undertake an analysis of pain-related care focused on utilization linked to pain conditions, identified by diagnostic and procedure codes, and pain-related medications. Intervention costs include program implementation (e.g., training, meetings, and supervision; patient identification, invitation and screening) and delivery (e.g., online hosting, clinician calls). The analysis will take the perspective of the health plan (a principal decision maker for future implementation), so it will include all health system costs of intervention implementation and delivery in clinical settings.

Cost-effectiveness calculations. As we have done in prior economic evaluations of trials,²⁸ we will estimate the cost-effectiveness of the intervention using net benefit regression methods.^{29,30} This technique uses a "net benefits" framework, comparing the incremental cost-effectiveness ratio to a range of potential values for a decision maker's willingness-to-pay (WTP) for a unit of health gain. A cost-effectiveness acceptability curve (CEAC) is constructed that illustrates the intervention's probability of being cost-effective at various levels of WTP for a unit of outcome (e.g., cost per QALY of \$30,000 to \$100,000). The regression framework allows ready evaluation of cost-effectiveness in subgroups (following the intervention's findings). Net benefit regression uses as the dependent variable, net benefit: $nb_i = \lambda \cdot effect_i - cost_i$ (from person-level effect and cost data; λ = WTP level and is varied to construct the CEAC). We will perform sensitivity analyses to assess the applicability of costs to other settings, the estimation of replication costs, and economies of scale.³¹

Health care cost comparisons: We will undertake a comparison of the health care costs between the randomized groups. These comparisons will include overall, and pain-specific costs. The table below describes the proposed categories of health care costs. Health care costs will be analyzed using generalized estimating equations with appropriate link functions.

Categories of Health Care Costs to be Assessed		
	Pain-related ¹	Total
Prescription medications		
Ambulatory encounters		
Primary Care		
Physical Therapy, Occupational Therapy and / or Psychiatry ²		
Pain Medicine/Pain Clinic		
Mental/Behavioral Health or Addiction Medicine		
ER or Urgent Care		
Other specialty medical care ³		
In-patient hospital⁴		

1. Pain-related medications are identified by medication class (i.e., opioids, etc.). Pain-related in-person health care encounters are identified based on ICD-10-CM diagnostic codes.
2. Physical Therapy includes Physical Therapy, Occupational Therapy and Psychiatry visits.
3. Specialty medical care includes in-person encounters with any non-primary care department that is not already included in the table.
4. Pain-related hospitalizations have a primary (or principal) pain-related ICD-10-CM diagnostic code.

19.0. Safety Monitoring Analyses

Safety monitoring analyses will be prepared for the external Data Safety and Monitoring Board (DSMB) twice per year to align with the DSMB meeting schedule. **See the Study Protocol and Data and Safety Monitoring Plan for specific details on the data and safety monitoring procedures and reporting guidelines.**

Note that the behavioral interventions being evaluated in this comparative effectiveness trial have been widely used and evaluated in trials with a range of patient types who have similar clinical characteristics to the RESOLVE study population. The trial does not include the use or evaluation of any drug, device or experimental treatment.

19.1. Adverse Events

An adverse event (AE) is any untoward or unfavorable medical occurrence in a human subject, including abnormal signs, symptoms, or diseases, temporarily associated with the subject's participation in the research, whether or not considered related to the subject's participation in the research. Because the RESOLVE study population includes patients with chronic pain, who have fluctuating physical and emotional symptoms as part of the natural course of their condition, such symptoms will not be systematically solicited as part of the trial.

Specifically, AEs will be identified if participants proactively contact the study team at any time to self-report AEs or self-report during a regular study contact; or by intervention or study staff who are interacting with participants regularly throughout the intervention. Since AEs will not be solicited uniformly from all study participants, collection of these events will be biased by study arm (i.e., telephone CBT-CP participants will have greater interaction with study staff by phone and more opportunity to self-report these symptoms and events). AEs will be documented and tracked; a report of the frequency of AEs by site will be reviewed by the PI quarterly and provided to the DSMB on a semi-annual schedule.

Although we considered the possibility of examining other events of special interest particularly those of interest for the HEAL initiative overall (e.g., suicidality), we decided this was not advisable both because there is no clinical or empirical basis for hypothesizing that either of the active interventions would increase risk of events of special interest and because the unequal contact with study staff among participants in the different study arms inherently results in differential opportunities for ascertainment of "events." In this circumstance, between-group comparison of adverse events reported to or discovered by study staff would be biased and hence not meaningfully interpretable or actionable.

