2.4 Potential Risks and Benefits

2.4.1 Potential Risks

The RESOLVE study poses minimal risks. Those risks that might exist fall into four categories: (a) risks of the intervention; (b) risks associated with research assessments; (c) risks associated with potential loss of confidentiality; and (d) risks of worsening physical or emotional state. These minimal risks and the procedures to help mitigate the risks are described further below.

Risks associated with the intervention. The intervention programs consist of either an online program or virtual coach-led (telephone and/or video) CBT-CP sessions. CBT-CP focuses on helping people change how they think and act in response to pain-related stressors³⁸ and on increasing patients' coping skills to help them better manage their pain and improve their emotional and physical functioning. Therefore, individuals who participate in the interventions might experience emotional or physical discomfort related to challenges in modifying their thoughts and behaviors related to pain. For example, someone might feel discouraged or frustrated during the intervention process or they might be physically challenged by behaviors they try to address in increasing physical activity. However, these risks are minimal, in that the probability and magnitude of

discomfort is no greater than what someone might encounter in daily life. CBT-CP interventions have been used by the current study team and other investigators without adverse effects in studies as well as in clinical practice with patients with chronic pain and other health conditions.

Procedures to help mitigate these risks. All behavioral health staff who will be conducting the intervention sessions with participants will receive comprehensive training and supervision from one or more of the following individuals: Drs. [name] (PI), [name] (Co-Investigator at KPNW), and [name] (Co-Investigator at Duke University), all with considerable experience supervising and training the delivery of such clinical research interventions. Finally, participants who experience emotional or physical discomfort during the intervention have the option of seeking services in the participating health care system in which they are insured/served as well as outside of the health care system, if they prefer; enrollees can receive any pharmacologic or non-pharmacologic treatments available to them without restriction.

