13 STUDY OVERSIGHT

Study oversight will be under the direction of a Data and Safety Monitoring Board (DSMB) comprised of members with expertise in appropriate clinical, statistical, scientific, ethical disciplines.

The DSMB will meet before study enrollment begins and every six months thereafter, until the end of the study; to approve the study protocol prior to implementation; assess safety and effectiveness data; to monitor accrual of study participants; to study progress, and data integrity for the study. If safety concerns arise, ad-hoc meetings and more frequent standing meetings may be held.

The DSMB will operate under the rules of a charter that will be approved at the initial DSMB organizational meeting. At that time, data elements that the DSMB needs to assess will be clearly defined. The DSMB will provide recommendations to the funding agency, the National Institute on Aging, regarding proceeding with the study as planned, proceeding with modifications, or terminating the study, as noted in the DSMB Charter.

This study may be suspended or prematurely terminated if, in the opinion of the investigators or the NIA, there is reasonable cause. Written notification, documenting the reason for study suspension or termination, will be provided by the suspending, or terminating party. The investigators will promptly inform the IRB, providing the reason(s) for suspension or termination.

Circumstances that may warrant termination include, but are not limited to:

- Determination of unexpected, significant, or unacceptable risk to participants.
- Insufficient adherence to protocol requirements.
- Data that are not sufficiently complete and/or evaluable.

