8.0. Randomization

After completion of the baseline data collection, study participants will be individually randomized in equal ratio to one of the three study arms.

Randomization will be stratified on:

Variable	Source
Sex	Sex from electronic health record (Male vs. Female or Other)
Pain severity score	Score on BPI-SF from baseline survey (< 7 vs. ≥ 7)
Clinical site	KPWA, KPNW, KPGA, Essentia
Rural/medically underserved residency	Residency geocode for Census Tract from electronic health record

Within each stratum, to contain concealment and balance randomization over time, a random permuted block design will be used with random variable block sizes of 3, 6, or 9 to ensure approximately equal accrual into the three study arms.

The TIN JHU/Tufts Lead biostatistician will develop the randomization scheme and the TIN Utah DCC will implement the scheme using the appropriate statistical software. The scheme to be implemented will be integrated into the study centralized tracking system.

Randomization will be conducted by KPWHRI research staff within the study centralized tracking system after consent and baseline assessment completion.

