19.4. Descriptive Analyses

The safety analyses will be performed using descriptive statistics to quantify hospitalizations and deaths (SAEs) by usual care control arm and separately by each intervention arm. As the study is not powered to test for non-inferiority of the safety events by exposure to the interventions compared to the usual care control, no statistical tests will be performed on group differences in the SAE safety.

19.5. Summary of AEs and SAEs by MedDRA Code and Grouped by Organ System

Because this trial focuses exclusively on behavioral interventions MedDRA codes covering pharmaceuticals, biologics, vaccines, and drug-device combination products are not applicable.

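### Non-serious adverse events are planned for the DSMB as counts by site with no breakdown by arm, so that report cannot show an imbalance between arms

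*SAP*

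**What the plan says.** SAP 19.1 gives one format for adverse events that are not serious: "a report of the frequency of AEs by site will be reviewed by the PI quarterly and provided to the DSMB". Treatment arm is not mentioned. The section adds that these events are not solicited uniformly, and that collection will therefore differ by arm because coach-arm participants talk to staff more. In explaining why events of special interest are not examined, it also says that comparing staff-reported events between groups would be biased and could not be interpreted or acted on. Protocol 12.1.1 and 12.1.3 say much the same.

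Serious events are handled differently. SAP 19.2 finds deaths and hospitalizations by a health-record query in all arms every 6 months. SAP 19.3 summarizes them by type and treatment group, and SAP 19.4 describes "hospitalizations and deaths (SAEs) by usual care control arm and separately by each intervention arm", without tests.

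Three other places bear on the point:
- Protocol 2.4.1, on risks of the intervention, says that "individuals who participate in the interventions might experience emotional or physical discomfort".
- Protocol 13 has the DSMB assess safety data and lists "Determination of unexpected, significant, or unacceptable risk to participants" among the grounds for termination.
- SAP 2.0 allows data for the DSMB to carry arm codes A, B and C.

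**The concern.** Protocol 2.4.1 expects the interventions, if they do harm, to cause emotional or physical discomfort. Unless that led to admission or death, it would be an AE and not an SAE. The by-arm safety summaries therefore leave out the kind of harm the Protocol itself attributes to the interventions, and the one report that would contain it has no arm column.

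The other safeguards do not fill this gap. The relatedness scale in Protocol 12.1.5 and the notification rule in Protocol 13.1 apply to SAEs. Unanticipated problems (Protocol 12.2) and investigator review of AEs (Protocol 20.1) work case by case and do not compare arms. If the by-site report is all the DSMB receives on AEs, an excess in one program would not be visible to it.

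**Working it through.** The plan states no AE rate or AE count, so there is no figure of its own to reproduce. The rates and capture probabilities below are assumptions chosen for illustration.

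**Inputs from the documents**
- Randomized: 2,331, or 777 per arm (SAP 5.0). Check: 621 / 0.80 = 776.25, rounded up to 777.
- Allocation (SAP 8.0): "study participants will be individually randomized in equal ratio to one of the three study arms".
- Sites (SAP 8.0): "KPWA, KPNW, KPGA, Essentia". Site is one of four stratification factors, and within strata "a random permuted block design will be used with random variable block sizes of 3, 6, or 9".

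**Step 1: participants per site.** Assume four equal sites with equal AE rates. Then 2,331 / 4 = 582.75 per site, and 582.75 / 3 = 194.25 per arm within a site. Unequal sites would scale the totals but would not add information on arm.

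**Step 2: expected events by site and by arm.** Assume 6% in one arm and 2% in the other two.
- Per site: 194.25 × (0.06 + 0.02 + 0.02) = 19.4
- Per arm: 777 × 0.06 = 46.6 and 777 × 0.02 = 15.5
- Even spread at 3.33%: 582.75 × 0.0333 = 19.4 per site, and 777 × 0.0333 = 25.9 per arm

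| Where the excess lies | Expected per site | painTRAINER | Coach | Usual care |
|---|---|---|---|---|
| painTRAINER | 19.4 | 46.6 | 15.5 | 15.5 |
| Coach | 19.4 | 15.5 | 46.6 | 15.5 |
| Usual care | 19.4 | 15.5 | 15.5 | 46.6 |
| Nowhere | 19.4 | 25.9 | 25.9 | 25.9 |

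The site column is the same in every row.

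**Step 3: simulation.** This used 4,000 trials with 194 participants per arm at each of four sites, at most one event per person, full capture, and a chi-square test at 0.05. The test serves only to show how much information each layout holds; no test is proposed for the trial.
- Excess in painTRAINER: the by-site comparison rejected in 4.8% of runs, the by-arm comparison in 99.6%.
- Excess in the coach arm: 4.3% and 99.4%.

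The by-site figures are about the false-positive level.

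**Step 4: what unequal capture does to a by-arm table.** Assume a true rate of 6% in every arm, so expected recorded events are 777 × 0.06 × capture probability.
- Capture 30% painTRAINER, 60% coach, 30% usual care: 14.0, 28.0 and 14.0.
- Capture 40%, 80% and 30%: 18.6, 37.3 and 14.0.

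Neither case has a true difference, yet both tables look unbalanced. In the second, painTRAINER also exceeds usual care.

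**The case against.** The strongest reply is that the sponsor considered this and declined. The sentence in SAP 19.1 closes the discussion of events of special interest, but its wording covers staff-reported AEs in general and is not confined to formal tests. Step 4 shows that the worry is justified. This part stands: a by-arm table could not establish that a program causes harm.

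The second reply is that the documents do not say the by-site report is all the DSMB gets. SAP 19.0 and Protocol 15.10 defer reporting detail to the Data and Safety Monitoring Plan, and Protocol 13 leaves the DSMB's data elements to the meeting that approves its Charter. Neither document was available. This also stands, and it limits the point to what the Protocol and SAP specify.

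The third reply is that little is at stake. Protocol 2.4.1 rates the discomfort as no more than that of daily life, and events leading to admission or death are shown by arm. This keeps the matter modest, but it does not explain an AE report to the DSMB that has no arm column.

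A reader might also infer more than the documents support:
- **That stratifying by site is the cause.** It is not. Unstratified 1:1:1 allocation would also give similar arm mixes at each site. The cause is the missing arm column.
- **That an excess in painTRAINER would be a true signal because contact is greatest in the coach arm.** Protocol 10.1.1 gives painTRAINER users an onboarding call, and follow-up calls that look for the reason for non-adherence. An excess over usual care could be capture alone, and such calls may draw out reports of discomfort.
- **That AEs given as the reason for withdrawal depend less on contact.** Nothing supports this. Protocol 9.1 and 9.2 record reasons when participants tell staff, and Protocol 9.3 and 10.1.2 give the active arms repeated outreach after missed sessions.

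**Conclusion.** The point holds for non-serious AEs. The Protocol and SAP specify counts by site and no breakdown by arm, and under 1:1:1 allocation those counts carry essentially no information on which arm has an excess. Under the assumed rates, a threefold excess in one arm leaves every site at about 19.4 expected events. The exact figures rest on assumed rates, equal sites and full capture; the conclusion that site totals do not identify the arm does not depend on the particular rates.

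It does not extend to SAEs, which are summarized by treatment group. Nor does it show that the DSMB will lack this information, since the Data and Safety Monitoring Plan or the Charter may supply it. Unequal capture is a reason for a caveat, for no tests and for no causal reading; it does not require leaving arm out of a closed report. This is a cheap improvement to safety reporting, not a flaw in the trial's effectiveness analysis.

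**What to change.** Keep the by-site report for the PI. In SAP 19, add a descriptive table of AEs by coded arm and by the severity grades of Protocol 12.1.4, for the closed DSMB report and again for the final safety section. The table should:
- show how each AE came to light, using the three routes in Protocol 12.1.1 (contact started by the participant, regular study contact, reason for withdrawal or dropout);
- carry a footnote on unequal ascertainment that covers the coach arm and also the painTRAINER onboarding and follow-up calls;
- contain no tests.

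If the Data and Safety Monitoring Plan already provides this table, cite its section in SAP 19.1 instead.

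The cost is one table. Arm, AE and severity are already planned data. The documents do not say whether reporting route is held as a separate field, so it may need to be read from the AE record or shown as unknown. Counts of staff contacts per arm would help but are optional: Protocol 10.2 documents intervention-related contacts, and usual-care contacts may not be recorded. The downside is that a difference between arms may reflect capture and not harm, which the footnote discloses.

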19.2. Serious Adverse Events

For this comparative effectiveness trial, a serious adverse event (SAE) is defined as an event that:

- Results in death during a patient's active participation in the trial.
- Results in inpatient hospitalization during a patient's active participation in the trial. (Planned hospitalization scheduled before the enrollment of a study participant is not an SAE.)

Given the relatively large sample size for this trial (N=2,331), we expect some inpatient hospitalizations and deaths to occur among participants. However, none of our previous trials using these types of behavioral interventions have identified study related SAEs.

The following is a summary of the procedures that will be used for monitoring and reporting SAEs; further detail is provided in the DSMP.

Each clinical site will query active participants' electronic health records data every 6 months (in alignment with the DSMB meeting schedule) to identify any deaths or hospitalizations throughout the interval of active participant enrollment in the trial.

For deaths, the date of the event and information needed to facilitate the chart review (described below) will be extracted. For hospitalizations, diagnoses, reason for admission, and length of stay will be extracted to allow the determination of potential relatedness.

A physician within each health care system/clinical site will conduct a chart review for each death to assess its potential relatedness to study procedures and interventions. The findings of each review will be entered into a DSM electronic data capture system hosted by the DCC.

Hospitalizations will not be chart reviewed routinely, however if reports suggest possible relatedness, chart reviews will be conducted on all or a subset of hospitalizations based on DSMB recommendation.

A report summarizing the SAEs and chart reviews will be provided to the DSMB at regular meetings. Any SAEs that are identified during these semi-annual reviews which meet the criteria for immediate reporting to the IRB, NIA PO, and DSMB will be reported according to DSMP procedures.

In addition to the semi-annual EHR queries, SAEs (hospitalizations and deaths) may be identified by participant self-report. If this occurs, the event will be documented and reviewed by the designated physician at the clinical site as part of the semi-annual review described above; it will not be reviewed at the time of reporting.

